## DURABLE-I STUDY:

### DIELECTRIC UNRAVELLING OF RADIOFREQUENCY ABLATION EFFECTIVENESS

#### Study Purpose

The purpose of this study is to evaluate real-time gap detection using EPD D700 dielectric sensing compared with customary electrical isolation tests and Adenosine infusion at the end of the procedure. Furthermore, safety, usability and clinical applicability of the system for guided AF ablation will be confirmed.

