#### Study Design

Prospective, single-center, non-randomized, non-blinded, open label, and single arm study.

All procedures will be performed under CARTO 3 guidance for the treatment of atrial fibrillation (AF). The EPD D700 system will be used interchangeably, to record pre-, during and immediate post-ablation tissue characteristics and compute likelihood of lesion transmurality and permanency. Additionally, D700 system safety, feasibility, usability and clinical applicability will be documented.

The entire procedure will be conducted as customary, using standard and approved off-the-shelf equipment (body surface electrodes, diagnostic and irrigated ablation catheters, RF generator and recording system), in a completely clinically independent manner from the EPD D700 system. The physician will neither use nor rely on any of the D700 system output for clinical decision making and will be blinded to the D700 lesion assessment forecasts. One month following the initial procedure, a repeated procedure will be performed for gap detection and its results will be correlated with the D700 predictions.

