- Before, during and immediately after each ablation point, the EPD D700 system will record (for a few seconds) specific dielectric characteristics from the catheter tip. These readings, reflecting estimated transmurality and probability of the lesion's permanency, will be analyzed in the post-procedure phase and will not be considered by the user during the procedure.
- Thirty minutes after the completion of the full ablation plan, a formal acute electrical isolation test will be performed to identify remaining gaps.
- IV Adenosine infusion, a bolus of 12-18mg, will be performed to identify additional existing dormant conduction.
- Touch-up ablations will be added according to the two previous tests' findings.
- The procedure will be concluded only after the physician has decided there are currently no remaining identifiable gaps and the PVI is, based on current knowledge, deemed durable.

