**Data to be collected during the procedures:**

- Overall procedure time.
- Overall EPD D700 set up time.
- Fluoroscopy time.
- Acute (during and immediately after the procedure) AE/SAE Evaluation.
- Full CARTO3 location data (CARTO3 export file).
- Full CARTO3 Point List and Tags.
- Pre-ablation, during and Immediate Post-ablation lesion assessment at each ablation point.
- Each ablation site location will be tagged on both CARTO3 and EPD D700 maps.
- As SmartTouch® is used, contact force data will also be recorded.
- Recording system data.

*This document was created using  
Solid PDF Tools  
http://www.SolidDocuments.com/  
To remove this message, purchase the product at*

MASTER

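### The stated purpose is real-time gap detection, but the plan dates D700 analysis after the procedure and never makes a live output the value tested

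*Combined protocol and SAP*

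**What the plan says.** Study Purpose: "The purpose of this study is to evaluate real-time gap detection using EPD D700 dielectric sensing". The comparators it names are the usual isolation tests and adenosine, both applied at the end of the procedure.

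Study procedures, first AF ablation procedure: around each ablation point, "the EPD D700 system will record (for a few seconds) specific dielectric characteristics from the catheter tip". These readings are described as reflecting transmurality and lesion permanency, and they "will be analyzed in the post-procedure phase and will not be considered by the user during the procedure".

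Study Design: the D700 is used to "compute likelihood of lesion transmurality and permanency", with no statement of when the computation takes place. The physician "will be blinded to the D700 lesion assessment forecasts". A repeat procedure at one month looks for gaps, and "its results will be correlated with the D700 predictions".

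Data to be collected during the procedures: the list includes "Pre-ablation, during and Immediate Post-ablation lesion assessment at each ablation point".

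**The concern.** A real-time claim means that the system can flag a likely gap while the catheter is still in place and the operator could act on it. The comparators named in the purpose meet that standard: the isolation test and adenosine are read during the first procedure, and touch-up ablation follows from their findings. A D700 result worked out afterwards is not being compared on the same footing. An offline analysis could in principle draw on the complete map, on points ablated later, or on cleaned recordings, none of which is available at the moment of ablation.

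What is at stake is the conclusion the trial can support. If the value that enters the month-1 comparison is a post-procedure one, good agreement says that signals acquired live carry information about later gaps. It does not say that the system can deliver that information in time, and delivery in time is what the purpose sets out to evaluate.

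**Working it through.** No arithmetic applies: the protocol gives no target accuracy or power calculation on this point, and the question is one of timing. The check is to follow the D700 value from recording to comparison and ask at each step whether the text fixes its time.

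1. **Recording.** Study procedures is explicit that signals are captured around each ablation point, for a few seconds. Acquisition is live.
2. **Computation of a likelihood or forecast.** Study Design says the D700 computes likelihoods and that the operator is blinded to forecasts. It does not say whether these are produced at the point, later in the same session or afterwards.
3. **Analysis.** Study procedures places analysis of the readings in the post-procedure phase. No other text dates the analysis.
4. **Collection.** The list of procedural data includes a lesion assessment at each point. That is consistent with a live output, but the list does not say whether the item is a computed call or the raw reading. It has no item for the time at which an output became available, or for whether one was produced at all.
5. **Fixing the value.** Nothing requires a D700 call to be generated, time-stamped or stored unchanged before the 30-minute isolation test, the adenosine bolus or the month-1 procedure.
6. **Comparison.** Study Design correlates the month-1 findings with D700 predictions and does not define them. Three outputs could qualify: the optional point-level forecast prepared from imaging before the procedure (Study procedures, CT/MR post-processing), an output generated during the procedure, and the post-procedure analysis.

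Only step 1 is fixed as live. Step 3 is fixed as not live. Steps 2, 4 and 6 are open, and step 5 is absent. A team could follow the protocol to the letter and never test a real-time output.

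**Can the effect be sized?** No. That would need the proportion of points without a usable live output, the accuracy of live and offline outputs, and a rule for turning point-level outputs into segment-level calls. The documents give none of these. Multiplying an assumed offline sensitivity by an assumed proportion of points with live output would not work either. Gaps are reported in 8-16 segments and ablation points lie 5-6 mm apart, so a segment may hold several points. Losing one point need not lose a gap, and points without a gap do not enter sensitivity.

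**The case against.** The strongest reply is that 'analyzed' may mean only that estimates produced during the procedure are evaluated afterwards, as in any blinded accuracy study. Blinding the operator to forecasts makes most sense if forecasts exist during the procedure, and the data list points the same way. 'Real-time' may also mean only that signals are acquired lesion by lesion, in contrast to tests done at the end, and the protocol does specify that.

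Much of this stands. A reader might infer that no live output exists and that real-time performance is certainly untested. The documents do not support that, because Study Design and the data list leave room for a hidden live value. A reader might also infer that Study procedures sends the post-procedure analysis to the month-1 comparison. It does not: the link is made in Study Design, with the predictions left undefined. Nor does any text provide for dropping or repairing recordings, or for leaving out points without live output. The missing-output rule is unspecified, not unfavourable by design.

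The reply does not remove the gap. Blinding requires that output be hidden, not that its analysis be deferred, and Study procedures states the two separately. If the intended meaning is live acquisition with later analysis, the purpose should say so, because as written it speaks of real-time detection. If a live value exists, the protocol still has to name it as the one tested.

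**Conclusion.** The concern holds as a mismatch between the stated purpose and the value the plan commits to testing. Followed as written, the plan can show how accurate post-procedure analysis of intra-procedural signals is. It does not secure evidence of real-time detection. This rests on reading 'real-time gap detection' as detection available during the procedure, and on Study procedures being the only text that dates the analysis.

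No size of bias can be given. It would be tempting to say that reported accuracy will be inflated for real-time use, but that is a risk and not a finding, because the plan contains neither a missing-output rule nor a reporting rule. The purpose in question is the study's leading stated one; the protocol labels no primary endpoint.

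The point should be settled before analysis begins. It limits the claim, but it does not invalidate the study, which can still yield sound evidence on offline accuracy.

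**What to change.** Amend Study Purpose, Study Design and Study procedures so that claim and method agree, in one of two ways.

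**(a) If the on-site system generates an output during the first procedure.** Define the D700 prediction used for the real-time claim as that per-point output, hidden from the operator and stored unchanged before the 30-minute isolation test. Touch-up points come after that test, so state a separate storage time for their outputs. Report points that lack an output and count them as no detection in the real-time analysis. Appendix 1 describes a mode in which the catheter and patches are connected to CARTO3 alone, so show points unrecorded for that reason separately and do not merge them with device failures. Report any later reprocessing separately, labelled offline.

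**(b) If no such output exists.** Remove 'real-time' from the purpose and describe the study as evaluating post-procedure analysis of recordings made during the procedure.

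Option (a) costs a little more analysis work, a storage step, and possibly a less favourable reported accuracy. Option (b) changes wording only and narrows the claim. Neither alters patient care, operator blinding or enrolment.

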## Appendix 1: CARTO3 and EPD D700 operating in-tandem

This appendix describes the connection between D700 system and CARTO3 (Biosense Webster JNJ) system that was especially developed in order to enable temporary operation of the two systems in-tandem. This is a requirement that must be met merely in the interim phase until users gain full confidence in D700's accuracy and reliability. The connection between the two systems is accomplished by two EPD external boxes:

- EPD CARTO3 Cat box
- EPD CARTO3 Patch box

There are two operational modes enabled while using these connection boxes:

- a. CARTO3 mode:

In this mode the CARTO3 is connected as stand-alone system and retains all its customary functionalities using both EM and Impedance-based localization.

- b. D700 mode:

In this mode the system toggles the RF generator and the body surface patches to the D700 system, while disconnecting the CARTO3 from the ablation catheter and the body surface patches. Dummy loads are connected to CARTO3 system as inputs. In this mode, although an error message might appear on CARTO3 screen, the CARTO3 is still using its magnetic location and the navigable catheters equipped with a magnetic sensor will still be visualized.

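### The Study Purpose promises to confirm the D700's usability and clinical applicability for guided ablation, but the procedures are CARTO3-guided and no listed data item measures guided use

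*Combined protocol and SAP*

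**What the plan says.** After the gap-detection aim, the Study Purpose adds a second one: "safety, usability and clinical applicability of the system for guided AF ablation will be confirmed".

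The Study Design states that aim differently: "D700 system safety, feasibility, usability and clinical applicability will be documented". There the verb is weaker, feasibility is added and guided ablation is not mentioned.

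On conduct, the Study Design places all procedures under CARTO3 guidance and has them run "in a completely clinically independent manner from the EPD D700 system". It continues: "The physician will neither use nor rely on any of the D700 system output for clinical decision making". The operator is also blinded to the D700 lesion forecasts. The Study procedures section says of the D700 readings that they "will be analyzed in the post-procedure phase and will not be considered by the user during the procedure". The second procedure, one month later, is again under CARTO3 guidance.

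One part of the text points the other way. The Study procedures section lists optional recommended isolation lines among the outputs of the pre-procedure image processing. It also lets the operator navigate to a first ablation point that may be chosen either by the user or by computer recommendation.

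The list of data to be collected includes "Overall EPD D700 set up time", overall procedure time, fluoroscopy time, acute adverse events, lesion assessments at each ablation point, and tagging of each site on both maps. Appendix 1 describes the in-tandem connection as needed "merely in the interim phase until users gain full confidence in D700's accuracy and reliability".

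**The concern.** To confirm that a system is usable and clinically applicable for guiding ablation, someone has to guide ablation with it and the result has to be measured against something. The Study Design keeps D700 output out of the operator's decisions. That suits the main aim, because blinded forecasts can be compared fairly with the gaps found at one month. It also means that the same procedures cannot show how the system performs when its output is used.

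What is at stake is the secondary conclusion. A report written to the Study Purpose could state that usability and clinical applicability for guided ablation were confirmed, on data from procedures that another system guided. The time measures do not fill the gap. They come from an interim tandem arrangement, and overall procedure and fluoroscopy times mix CARTO3 work with D700 set-up and switching between modes. The main gap-prediction aim is not affected.

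**Working it through.** This is mainly a comparison of text, with a small amount of arithmetic.

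**1. The plan's own figure.** Study Population expects 24 patients, of whom 4 decline: 24 − 4 = 20. This reproduces the stated 20. The documents give no alpha, power, precision target or success criterion, so there is no sample-size formula to check.

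**2. Observations of guided use.** Two kinds of guidance need to be kept apart.

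| Kind of guidance | What the text provides | Patients contributing an observation |
|---|---|---|
| Clinical decisions based on D700 output during the procedure | Ruled out by the Study Design; readings analysed afterwards under Study procedures | 0 of 20, if the plan is followed |
| Following pre-planned recommended lines or a recommended first point | Optional under Study procedures; in tension with the Study Design | Unknown, anywhere from 0 to 20 |

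The second row stays unknown after the trial as well, because no listed data item captures whether a recommendation was offered or taken.

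**3. The data list against the claim.** The list has ten items. Three relate specifically to the D700:

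- set-up time;
- lesion assessment before, during and after each ablation point (Study procedures says that the D700 makes these recordings);
- tagging of sites on the D700 map as well as the CARTO3 map.

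These can describe set-up burden and completeness of recording in tandem operation. Acute adverse events can describe safety in that configuration. The list has no operator rating, usability scale, applicability measure or criterion for guided use.

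**4. The two statements of the aim.** The Study Purpose has confirmation and guided ablation. The Study Design has documentation and no guided ablation. Only the Study Design wording is close to what steps 2 and 3 can deliver.

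**5. Safety, as a side check on the word confirmed.** The sentence also covers safety. Assume, for illustration only, that no patient out of 20 has a given event. The exact upper 95% limit on the event rate is then:

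- one-sided: 1 − 0.05^(1/20) = 13.9%;
- two-sided: 1 − 0.025^(1/20) = 16.8%.

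Even a clean result would leave rates of this size compatible with the data, so a descriptive verb fits safety better too. The point about guided use does not depend on this step.

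**The case against.** The strongest reply is that the documents do not uniformly exclude guidance. The Study procedures section provides recommended lines, registers the images with the D700, allows a computer-recommended first point, and then has the operator move along the line in its planned order. These steps bear on planning and navigation. This part of the reply stands in one respect: the text is inconsistent with the independence statement in the Study Design, and it does not say whether a pre-planned recommendation counts as D700 output. It does not support confirmation, because the recommendations are optional and nothing on the data list records or evaluates their use.

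A reader might go further and infer that the D700 only listens and that up to 2 × 20 = 40 procedures contain no guided ablation. The documents do not support that reading:

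- Appendix 1 routes the RF generator and the body surface patches through the D700 connection boxes, so the system is physically active.
- The second procedure is a remapping and gap check that names no D700 step, so it should not be counted as a missed opportunity.
- The optional recommendations leave open whether planning was influenced.

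Nor does it follow that usability goes wholly unexamined. Patch deployment, registration, mode switching and set-up all take place and bear on usability in tandem operation.

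Two further replies have some weight. The Study Design says only documented, so a sponsor following that section would not claim confirmation; the defect lies in one sentence of a secondary aim and its disagreement with the design section. And descriptive documentation needs no comparator, so the single arm is not a fault in itself. It becomes one only if procedure times are used to confirm something.

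Finally, the words about guided ablation may merely describe the system's intended use. The sentence would still promise to confirm usability and applicability for that use, which the Study Design tells the operator not to exercise.

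**Conclusion.** The sentence in the Study Purpose is wrong as written. Under the Study Design, 0 of 20 patients yield an observation of clinical decisions guided by D700 output, and no listed measure or criterion could turn the remaining data into confirmation of guided use. This assumes that the independence and blinding statements are followed. If pre-planned recommendations are followed in some patients, the conclusion is unchanged, because that use is neither recorded nor assessed.

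The point is limited to an unsupported secondary conclusion and to two sections that disagree. No estimate, error rate or sample size changes. The design can still describe safety, technical feasibility and usability in tandem operation, and it can still compare blinded forecasts with later gaps. The wording should be corrected before results are reported.

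**What to change.** - **Study Purpose.** Replace the second sentence with: *Furthermore, safety, technical feasibility and usability of operating the D700 in tandem with CARTO3-guided AF ablation will be described.*
- **Study Design.** Limit usability and clinical applicability to in-tandem recording, so that both sections state the same aim.
- **Reporting.** Tie the aim to data already listed: acute adverse events and serious adverse events, D700 set-up time, and the proportion of ablation points with a complete D700 assessment before, during and after ablation.
- **Limits.** State that usability and clinical applicability for D700-guided ablation are not tested here and need a later study.
- **Consistency.** Reconcile the Study Design and Study procedures sections on whether D700-derived recommendations may influence the procedure.

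The cost is a narrower secondary claim, edits to the wording, and one extra tabulation of data already recorded. No extra patients or procedures are needed.

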#### Study Design

Prospective, single-center, non-randomized, non-blinded, open label, and single arm study.

All procedures will be performed under CARTO 3 guidance for the treatment of atrial fibrillation (AF). The EPD D700 system will be used interchangeably, to record pre-, during and immediate post-ablation tissue characteristics and compute likelihood of lesion transmurality and permanency. Additionally, D700 system safety, feasibility, usability and clinical applicability will be documented.

The entire procedure will be conducted as customary, using standard and approved off-the-shelf equipment (body surface electrodes, diagnostic and irrigated ablation catheters, RF generator and recording system), in a completely clinically independent manner from the EPD D700 system. The physician will neither use nor rely on any of the D700 system output for clinical decision making and will be blinded to the D700 lesion assessment forecasts. One month following the initial procedure, a repeated procedure will be performed for gap detection and its results will be correlated with the D700 predictions.

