#### Study Population

Twenty-four Paroxysmal Atrial-Fibrillation (PAF) patients, amenable to catheter-based AF ablation therapy comprising of Pulmonary Veins Isolation (PVI). We suggest that 4 will patients decline to participate. The overall number of patients in the study is twenty.

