### DURABLE - 1st Procedure

[figure not shown]

Figure 1: Step-by-step 1st procedure, using both CARTO3 and D700 interchangeably.

■ **Second AF ablation procedure (Figure 2):**

- The second procedure will be conducted 1 month after the initial procedure in a similar set up under CARTO3 guidance.
- After repeated registration, with the previous pre-acquired 3D image, the LA will be remapped.
- In order to functionally identify existing gaps, remaining gaps will be sought for by electrical functional test.

MASTER

- If such gaps will be encountered, the physician will apply the customary touch-up approach.
- The location of gaps around the PVs will be reported in 8-16 segments (Figure 3).

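### The month-1 comparison names only correlation, which cannot show whether the D700's stated probability of lesion permanency is at the right level

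*Combined protocol and SAP*

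**What the plan says.** Study Design states that the D700 will "compute likelihood of lesion transmurality and permanency". Study procedures describes the per-point readings as "reflecting estimated transmurality and probability of the lesion's permanency", to be analysed after the procedure. The operator is blinded to these forecasts and does not act on them.

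The one analysis named for the month-1 outcome is that "a repeated procedure will be performed for gap detection and its results will be correlated with the D700 predictions". The plan gives no coefficient, unit of analysis, cut-off or success criterion. It mentions no comparison of predicted with observed gap rates. For the second procedure, "The location of gaps around the PVs will be reported in 8-16 segments".

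Study Purpose also sets an acute comparison, to "evaluate real-time gap detection using EPD D700 dielectric sensing compared with customary electrical isolation tests and Adenosine infusion at the end of the procedure". No statistic is named there either.

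**The concern.** A quantity described as a probability makes two claims: that sites with higher values hold more often, and that the value itself is right. Correlation addresses only the ordering of sites. If every forecast is pushed towards permanent while the order of sites is kept, rank correlation and AUC do not move, and Pearson correlation moves little or not at all.

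A good correlation at one month could therefore be read as support for the stated likelihoods although their level was never examined. This matters because Study Purpose includes confirming clinical applicability for guided ablation, and Appendix 1 describes tandem operation as an interim phase until users trust the system's accuracy. A forecast that sorts sites well but understates gap risk several-fold should be reported differently from one that is also right in level.

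**Working it through.** **The plan's own figure.** Study Population gives "Twenty-four Paroxysmal Atrial-Fibrillation (PAF) patients" and "We suggest that 4 will patients decline to participate": 24 − 4 = 20 patients. No gap rate, effect size, alpha or power is stated, so there is no power-based figure to reproduce.

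**Inputs.**
- From the documents: 20 patients and 8 to 16 segments. Reading the segments as per patient (an assumption) gives 20 × 8 = 160 to 20 × 16 = 320.
- Assumed: 10% gap rate per segment (5% to 20% in step 3), and true log-odds of a gap normally distributed with SD 1.

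**Step 1: shift the level, keep the ranking.** In a simulation of 1,000,000 segments the true gap risk was p = 1/(1 + exp(−(a + z))), with z standard normal and a set so that the mean is 10%. The forecast used the same z with a lower a. Expected gaps = 320 × mean stated risk.

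| Mean stated gap risk | Spearman | AUC | Pearson | Expected gaps in 320 | Gaps at the true 10% rate |
|---|---|---|---|---|---|
| 10% | 0.258 | 0.748 | 0.302 | 32 | 32 |
| 6% | 0.258 | 0.748 | 0.301 | 19.2 | 32 |
| 3% | 0.258 | 0.748 | 0.297 | 9.6 | 32 |
| 1% | 0.258 | 0.748 | 0.290 | 3.2 | 32 |

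A different assumed risk distribution (Beta, concentration 6, 10% gap rate) gives the same result. With p now the permanency probability, the forecast 0.9 + 0.1p states a mean gap risk of 1% and has the same Pearson (0.376), Spearman (0.327) and AUC (0.816) as the calibrated forecast.

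**Step 2: where the argument stops.** Under the assumptions of step 1:
- Tripling the log-odds lowers Pearson from 0.30 to 0.22; rank measures do not move.
- Understating risk (log-odds −2.3) in a random half of sites lowers Pearson to 0.20 and Spearman to 0.17.
- With a cut-off fixed beforehand at a stated gap risk of 10%, sensitivity falls from 0.68 to 0.44, 0.16 and 0.01 down the four rows of the table.

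**Step 3: is a level check informative at this size?** O/E is observed over expected gap-bearing segments. With variance doubled for clustering (assumed), the approximate 95% interval is O/E × exp(±1.96 × √(2/O)). The table sets O at its expectation.

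| Segments, gap rate | O | 3.3-fold understatement: E, interval | 1.7-fold understatement: E, interval |
|---|---|---|---|
| 160, 5% | 8 | 2.4, 1.25 to 8.9 | 4.8, 0.63 to 4.4 |
| 160, 10% or 320, 5% | 16 | 4.8, 1.67 to 6.7 | 9.6, 0.83 to 3.3 |
| 160, 20% or 320, 10% | 32 | 9.6, 2.04 to 5.4 | 19.2, 1.02 to 2.7 |
| 320, 20% | 64 | 19.2, 2.36 to 4.7 | 38.4, 1.18 to 2.4 |

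The larger error excludes 1 in every row. The smaller one does not at 8 or 16 gaps, and only just does at 32. These are intervals at the expected count, not power figures. In the first row the log ratio is ln(3.33)/√(2/8) = 1.20/0.5 = 2.4 standard errors from zero, so even that error could be missed by chance.

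**The case against.** **The word may be loose.** In a design summary, being correlated with can simply mean compared with, and no coefficient is given. That is fair: the firmer finding is that the month-1 analysis is unspecified. The point survives because naming a coefficient or an AUC would still leave level unexamined.

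**A reader might infer that correlation is blind to any error in the forecast.** It is not. Step 2 shows that reversals, shuffling and uneven errors change it, and that strong over-confidence lowers Pearson.

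**A reader might infer that level would stay untested whatever accuracy measure is chosen.** It would not. A cut-off set in advance on the stated probability exposes a shift, as the fall in sensitivity shows.

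**A reader might infer that the study tests the D700 in no other way, or would declare it validated.** Study Purpose adds the acute comparison, though it names no method and does not address one-month permanency. No success criterion exists against which validation could be declared.

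**The output scale is undefined.** The documents do not say that a percentage is displayed, and the operator may not use the forecasts in this study. Any harm is therefore to later interpretation, not to these patients' treatment.

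**Lesion permanency and a segment gap are different events.** Ablation points lie 5-6 mm apart, so a gap may fall between two permanent lesions and raise O/E without any error in the point forecasts. This stands. It rules out a rule that would automatically demote the output to a ranking score whenever the interval excludes 1.

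**Conclusion.** The concern holds in limited form. For the month-1 outcome the plan names only correlation, although the output is described as a probability, and correlation cannot detect a forecast that ranks sites correctly but states the wrong level of risk. In the illustration, a 10-fold understatement costs 0.012 in Pearson (0.302 − 0.290) and nothing in Spearman or AUC, against a 10-fold shortfall in expected gaps.

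The invariance of rank measures to an order-preserving distortion is a mathematical fact. The sizes rest on the assumed gap rate, log-odds spread, segment count and variance inflation, none of which the documents give. The documents do not show that the D700 is over-confident, only that the named analysis would not reveal it. The addition is worth making because it is cheap and could change what is concluded about the forecast; the study can run without it.

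**What to change.** In Study Design, state that month-1 gap results will be assessed for association with the D700 predictions and for agreement between predicted and observed gap rates. Then specify:

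- Observed versus expected gap-bearing segments (O/E), and the observed gap rate by forecast band, both with patient-level bootstrap intervals.
- The forecast recorded after the last RF application at each site, so that touched-up sites carry their final value.
- Where a segment holds several points, the expected count computed two ways: segment gap risk as 1 minus the lowest point forecast of permanency, and as 1 minus the product of the point forecasts. Report both.
- A statement that this is a coarse descriptive check, and that gaps between adjacent permanent lesions can also raise O/E. Attach no automatic relabelling rule to the result.

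The cost is one paragraph. Point-level lesion assessments and month-1 gap locations are already to be collected, so no extra patients or procedures are needed. The downsides are that a less favourable figure may have to be reported and that precision is limited with 20 patients.
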